3.0 Objectives

- Describe the study's purpose, specific aims, or objectives.
- State the hypotheses to be tested.
- Indicate the relevance to Veterans and the VA

The primary hypothesis is that anxiety outcomes, as measured by the GAD-7, and quality of life, measured by the SF-12 will be superior at 4-, 8-, and 12-month follow up for patients who are assigned to receive bCBT vs. EUC.

Primary Aim: To determine whether anxiety symptoms (GAD-7) and quality of life (SF-12) differ as a function of the intervention (bCBT for anxiety vs. EUC) at 4-, 8-, and 12-month follow-ups.

Secondary Aims: (Prediction of bCBT response and VVC-H use (bCBT group only)): A) To identify factors associated with bCBT response, namely whether bCBT is effective for specific anxiety disorders (e.g. generalized anxiety, panic, social phobia) and whether number of sessions received, and treatment engagement are critical to outcomes. B) To identify Veteran demographic and clinical factors associated with VVC-H use.

Exploratory Aims: A mixed-methods formative evaluation, informed by RE-AIM QuEST, will collect data related to Reach (#of Veterans receiving bCBT and VVC-H), Effectiveness (bCBT and VVC-H impact), Adoption (# of providers using bCBT and VVC-H), and Implementation (provider bCBT program fidelity and VVC-H potential). Data will be collected from qualitative interviews with Veterans and providers and integrated with quantitative data from provider surveys and chart reviews of bCBT and VVC-H use. With the ORD supplement to the main project, [name] will leverage the diverse Veteran populations included in the multisite

parent study (Houston, San Antonio, and New Orleans VA MCs) to understand barriers to treatment and research access for African American and Hispanic Veterans.

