Evaluation Framework: For this proposal, we chose a randomized pragmatic effectiveness trial to better align the intervention with standard VA clinical practices. To assess feasibility, acceptability, and preliminary implementation outcomes, we chose the mixed methods RE-AIM Qualitative Evaluation for Systematic Translation (RE-AIM QuEST) framework⁴ that expands on the original RE-AIM framework by highlighting complementary quantitative and qualitative outcomes for each of RE-AIM's 5 elements: Reach (participation rate of the targeted population), Efficacy/Effectiveness (impact of the intervention on outcomes), Adoption (system-level factors associated with intervention use), Implementation (intervention integrity and quality), and Maintenance (continuance of the intervention). Although this study focuses on effectiveness, we will also collect data from Veterans, providers, and VA clinic and operational leaders about the potential for the intervention to be implemented within VA settings.

All randomized participants will receive a note added to their medical charts. The note will provide information about the patient's anxiety symptoms and any actions being taken by the research team. Notes will provide information about the assessment process and will also indicate that the patient should continue to receive care as usual regardless of their study group assignment.

ARM #1: Brief CBT (bCBT):

[figure not shown]
Participants randomized to the bCBT direct referral arm will have their contact information and symptom information obtained from the assessment (e.g. responses from the GAD-7, etc.),

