5.4 Inclusion/Exclusion Criteria

- Describe the criteria that determine who will be included in or excluded from the study.

Veteran Participant Criteria:

Eligible Veteran participants are those who: 1) have received Primary Care Mental Health Integration services, or who are eligible for PCMH services (They are not receiving specialty mental health services) services at the Houston, New Orleans, or San Antonio VAMCs, 2) have a documented diagnosis of an anxiety disorder, and 3) endorse clinically significant symptoms of anxiety on two occasions to ensure consistency of anxiety symptoms (GAD-7 score of 10 or greater; telephone screen and baseline appointment). The GAD-7 is the current anxiety measure used by VA PCMH clinics and is appropriate for monitoring change in anxiety symptoms over time⁵.

Exclusion criteria are 1) cognitive impairment (documented diagnosis of a cognitive disorder in chart review or 3 or more errors on a 6-item cognitive screener), 2) bipolar or psychotic disorder (documented diagnosis in chart review or as assessed by the MINI 3) substance use disorders (document substance use disorder in chart review or assessed by the MINI or a score of 4 or more on the AUDIT-C), and 4) current receipt of psychotherapy for anxiety. For participants with a psychotherapy appointment within the last 3 months, we will confirm the treatment provided will not conflict with the study's intervention. Veterans receiving antidepressant medications at the time of enrollment WILL NOT be excluded.

Provider Criteria:

PCMH providers who conduct psychotherapy as part of their VA scope of practice will be targeted for recruitment. Clinicians will not be restricted based on discipline or prior CBT experiences but will be expected to have an interest in obtaining training and willingness to use bCBT in their practice. Providers will not be restricted based on profession. The only exclusion criteria for clinicians will be for those clinicians who are not appropriately authorized to provide psychotherapy as part of their scope of practice at the VA.

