5.6 Data Analysis

- Provide sample size determination and analysis (include anticipated rate of screen failures, study discontinuations, lost to follow-up etc.).
- Describe how, where and by whom the data will be analyzed.

Primary aim: Anxiety and Quality of Life differ as a function of bCBT for anxiety vs. EUC:

All analyses will be done on an intention-to-treat basis, and participants will be analyzed in the group to which they were randomized. We will first determine whether participants randomized

to the two study arms differed on baseline characteristics, age, race, gender, medical or mental health comorbidities, and anxiety. Chi-square tests will be used for categorical variables and t-test for continuous and ordinal variables.

We will examine the normality of the distributions of both primary outcomes and will consider transformations such as the log or the inverse. Because we are using an unequal randomization (see sample size section), it is especially important to test the assumption about the homogeneity of the variance of the residuals across the levels of the independent variables³⁷. For analyses of our primary outcomes, we will test the homogeneity assumption before testing for differences between the bCBT and EUC groups. If the assumption of equal variances is violated, we will use statistical tests such as the approximate t-test, which uses individual sample variances instead of the pooled variance. In addition, we will obtain Satterthwaite's approximation of the degrees of freedom. For the regression models, we will test whether the residual variances are equal and, if necessary, we will fit unequal variance models to obtain better estimates of the standard errors of the difference between groups. We will calculate the absolute differences in outcome measures between baseline and 12-month follow-up and the effect sizes of the bCBT group compared with EUC. We will also examine effect sizes for the bCBT group baseline vs. post-treatment and 8-month follow-up.

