To compare changes in anxiety symptoms between the two groups over time, we will use a longitudinal, mixed-model analysis containing terms for the intercept, treatment, time, and interaction between time and treatment. In separate analyses, we will compare changes in quality-of-life between the two groups over time using a similar mixed-model approach. The mixed-model analysis will allow us to nest patients by site. Any baseline characteristics found to be significantly different between bCBT and EUC will be included in the model, as will any differences in mental health service use. The four time points (baseline, 4-, 8-, and 12-month) will allow us to assess the immediate impact of treatment and the longer-term retention, improvement, or decay in outcomes. The treatment effect will measure differences between the intervention and control groups at baseline, and the time effect will measure whether there was an overall change over time in the outcome. The term of most interest will be the interaction between time and treatment, which will indicate whether there is a difference over time between the two groups. The use of the random-coefficient model will allow us to fit a line for each participant using his/her available data, including participants with missing values, and maximize the power to detect differences.

Secondary Analyses: Prediction of bCBT response and VVC-H use:

We will run two logistic regression analyses using only data from participants who received bCBT. In analysis 1, we will identify characteristics that predict response to treatment as defined as a reduction of 50% on the GAD-7. Predictor variables will include: baseline anxiety severity (GAD-7 score), presence of specific anxiety diagnoses (GAD, Panic, Social Anxiety, Other), medical comorbidities, and brief CBT-related factors (number sessions received and treatment engagement). In analysis 2, we will identify characteristics associated with VVC-H use. VVC-H

use will be classified as any (one or more VVC-H sessions) or none. Predictor variables will include: age, distance to VA facility in miles, medical comorbidities, depression and PTSD (presence or absence), and Veteran self-reported comfort receiving in-person VHA care and confidence using video-based services and technology.

Implementation Analyses (Exploratory):

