Analyses will use data from the mixed-method formative evaluation described above. Qualitative pre-implementation data will be analyzed using rapid qualitative analysis, a systematic and rigorous process, to provide data in real-time to tailor the intervention, and identify contextual barriers prior to rollout^{38,39,40}. Implementation and post-implementation interviews with providers and Veterans will be analyzed using directed content analysis⁴¹ consisting of deductive (a priori) codes from the RE-AIM QuEST framework. Inductive (a posteriori) codes that emerge from providers' and Veterans' experiences with the intervention and VVC-H delivery will also be identified. We will utilize Atlas.ti software to facilitate analysis and management of qualitative data. Quantitative data will be collected and analyzed as descriptive data.

Sample Size and Power Calculations

Primary Aim: To determine whether anxiety symptoms (GAD-7) and quality of life (SF-12) differ as a function of the intervention (bCBT for anxiety vs. EUC) at 4-, 8-, and 12-month follow-ups. A three-step sample-size calculation indicates that 225 anxiety patients will need to be randomized to draw conclusions regarding the primary hypothesis that bCBT will be superior to EUC at 4-, 8, and 12-month assessments.

Step 1: Power to detect GAD-7 differences. A sample size of 138 anxiety patients is needed to detect an effect size = 0.38 for the differences between bCBT and EUC GAD-7 outcomes using a two-sided t-test with 80% power at the .05 significance level, adjusted for repeated measures³⁷. The formula for the sample size, adjusting for repeated measures, is

$$N = \frac{2 * (Z_{(1-\alpha/2)} + Z_{(1-\beta)})^2 [1 + (T - 1) \rho]}{d^2 T}, \text{ where } N \text{ is the sample size per group, } Z_{(1-\alpha/2)} \text{ and}$$

$Z_{(1-\beta)}$ are the $(1-\alpha/2)$ and $(1-\beta)$ percentiles of the normal distribution, T is the number of follow-up measures, ρ is the correlation coefficient of the repeated measurements, and d is the effect size⁴². Solving this with $T = \text{three follow-up measurements after baseline}$, $d = 0.38$, and $\rho = .7$ yields a sample size per group of 69, and total sample $N^t = 138$.

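### At 4 and 8 months the plan specifies only before-after effect sizes within bCBT, and the mixed model names no between-arm contrast at those visits, although the primary hypothesis is superiority over EUC at each of them.

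*Protocol*

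**What the plan says.** Protocol 3.0 states the primary hypothesis between arms and by visit: anxiety and quality of life "will be superior at 4-, 8-, and 12-month follow up for patients who are assigned to receive bCBT vs. EUC". The sample-size part of 5.6 repeats that aim.

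The primary-aim text of 5.6, which the SAP carries unchanged, treats effect sizes in two consecutive sentences. The first promises the "absolute differences in outcome measures between baseline and 12-month follow-up and the effect sizes of the bCBT group compared with EUC". The second reads: "We will also examine effect sizes for the bCBT group baseline vs. post-treatment and 8-month follow-up". Table 4 in 5.5 marks the 4-month visit as post-treatment, so the second sentence concerns 4 and 8 months, and EUC is absent from it.

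The next paragraph of 5.6 (and of the SAP) gives the between-arm model: a longitudinal mixed model on four time points with treatment, time and their interaction. "The term of most interest will be the interaction between time and treatment, which will indicate whether there is a difference over time" between the groups. On how time enters: "The use of the random-coefficient model will allow us to fit a line for each participant". No contrast or effect size at 4 or 8 months is named.

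Two design features bear on how a before-after change reads. Entry needs a "GAD-7 score of 10 or greater; telephone screen and baseline appointment" (5.4). The chart note placed for every randomised participant says that "the patient should continue to receive care as usual regardless of their study group assignment" (5.1).

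**The concern.** Two of the three visits in the primary hypothesis have no specified estimate of bCBT against EUC. What is specified there is an uncontrolled change in one arm of a sample selected for high scores on the outcome itself. Scores chosen for being high fall on average at the next measurement without any treatment effect. Spontaneous recovery and other care can add to the fall. EUC participants complete the same assessments at the same visits, so the comparison that removes these components is available.

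The risk is in reporting. A before-after effect size at the end of treatment, printed beside a between-arm effect size at 12 months, is likely to be read as the same kind of quantity. If the one between-arm term is a linear slope, it can also miss a benefit that is largest at the end of treatment.

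**Working it through.** The plan gives no figure for this point, so there is none to reproduce. Two questions can be checked: how far a before-after change can move with no treatment effect, and whether the model as described supplies the missing contrasts.

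**1. Regression to the mean under no treatment effect**

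From the documents: GAD-7 of 10 or more at both screen and baseline (5.4); correlation of repeated measures 0.7 (5.6, sample size). Assumed, not in the documents: normal scores, equal correlation between all occasions, source-population mean μ of 8 to 13, SD of 4 to 5.

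Let m be the mean baseline score among those who pass both cut-offs. The expected later score is μ + [2ρ/(1+ρ)](m − μ), so the expected fall is (m − μ)(1 − ρ)/(1 + ρ). With ρ = 0.7 the factor is 0.3/1.7 = 0.1765. Simulating the double selection gives m:

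| μ, SD | m | Fall in points | Fall / unselected SD |
|---|---|---|---|
| 8, 5 | 13.94 | 5.94 × 0.1765 = 1.05 | 0.21 |
| 8, 4 | 13.05 | 5.05 × 0.1765 = 0.89 | 0.22 |
| 13, 5 | 15.74 | 2.74 × 0.1765 = 0.48 | 0.10 |
| 13, 4 | 14.88 | 1.88 × 0.1765 = 0.33 | 0.08 |

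The denominator matters. Divided by the narrower SD among those selected, the falls at ρ = 0.7 become about 0.11 to 0.40. The correlation matters too: with μ = 8, SD 5 and ρ = 0.5 the factor is 1/3, m is 13.88, and the fall is 5.88/3 = 1.96 points.

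**2. What a linear time-by-treatment term would report**

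Take visits at 0, 4, 8 and 12 months (mean 6, sum of squared deviations 36 + 4 + 4 + 36 = 80) and compound symmetry with ρ = 0.7. The fitted between-arm slope is Σ(t − 6)δ(t)/80, where δ(t) is the true between-arm difference in SD units.

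- Benefit appears by 4 months and holds, δ = 0, 0.38, 0.38, 0.38: slope = (−0.76 + 0.76 + 2.28)/80 = 0.0285 per month. The implied between-arm changes from baseline are 0.11, 0.23 and 0.34, against a true 0.38 at each visit.
- Early benefit, then decay, δ = 0, 0.57, 0.38, 0.19: slope = (−1.14 + 0.76 + 1.14)/80 = 0.0095 per month. The implied changes are 0.04, 0.08 and 0.11.

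Precision of the slope uses the 87 bCBT and 58 EUC participants to which the sample-size section works before inflating for clustering and attrition. SE = √[(0.3/80)(1/87 + 1/58)] = 0.0104. In the decay case z = 0.0095/0.0104 = 0.92, and power at two-sided 0.05 is Φ(0.92 − 1.96), about 15%. In the early-and-sustained case power is about 78%. The slope term then detects a difference but misstates its size at 4 and 8 months. A benefit that grows steadily (0.13, 0.25, 0.38) is recovered almost exactly, so the problem lies in the shape that the line imposes.

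**3. Precision of the missing contrasts**

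With 87 against 58, a raw between-arm effect size at one visit has a 95% half-width of 1.96 × √(1/87 + 1/58) = 0.33 SD. Power for 0.38 at one visit, two-sided 0.05, is about 61% unadjusted. With baseline adjustment it is about 74% if the baseline to follow-up correlation is 0.5, and about 88% if it is 0.7 (both assumed).

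**The case against.** The strongest reply is that the main analysis already answers the between-arm question. The mixed model uses every visit in both arms, the interaction is its key term, and 5.6 says the four time points serve to assess immediate impact and later retention or decay. The disputed sentence opens as an addition, and nothing calls the within-arm sizes a test of superiority. Most of this stands. A reader might infer that the plan discards the randomised control at 4 and 8 months, or has no between-arm analysis of those data. The documents do not support that. The gap is narrower: the model text names one interaction and a line per participant, and no contrast at either visit.

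It can also be said that the between-arm clause is not tied grammatically to 12 months. That is so. But it sits in the 12-month sentence, and the next sentence gives the other two visits a different quantity. If all visits were meant, the text needs the same edit.

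Finally, a reader might infer that regression to the mean is as large as the design effect of 0.38. The documents do not support that either. The source mean and SD appear nowhere in them. Values near 0.38 arise only by dividing by the SD of the selected sample, or by assuming a lower correlation and a source mean below the entry cut-off. The design's 0.38 is a between-arm difference and is not scaled to an SD truncated at 10.

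**Conclusion.** The point holds in this limited form. For 4 and 8 months the only effect sizes specified, on the natural reading, are within bCBT, and these are not treatment effects. That before-after changes include regression to the mean, and in which direction, follows from the entry rule. The size does not: about 0.3 to 1.1 points, or 0.08 to 0.22 of the unselected SD, rests on the assumed mean, SD, normality and correlation of 0.7, and leaves out recovery and other care.

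The mixed model makes a randomised comparison but, taken literally as linear in time, does not fill the gap when benefit comes early. That part depends on reading the line per participant as linear time. With categorical time the same model would give the contrasts. The trial's validity is not in question. Two of the three hypothesised visits lack a specified randomised effect estimate, and this should be put right before analysis.

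**What to change.** In Protocol 5.6 and the SAP primary-aim text, specify time as categorical in the mixed model. Report baseline-adjusted bCBT minus EUC differences and standardised effect sizes with 95% CIs at 4, 8 and 12 months, for GAD-7 and for SF-12, and name the SD used to standardise. Replace the sentence on bCBT-only effect sizes. If before-after changes are shown, show them for both arms and label them descriptive. State which visit contrast or contrasts are confirmatory.

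No new data, visits or participants are needed. The costs are a change in how time is coded, a few more model parameters, and a multiplicity decision, since three contrasts on two outcomes make six. Splitting alpha over three visits (0.05/3) would lower unadjusted single-visit power for 0.38 from about 61% to about 44%, which is a reason to settle the confirmatory contrasts in advance and to adjust for baseline.

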and through a weblink. They will also receive a letter encouraging them to discuss treatment options with their VA care providers (see Appendix 9). We will place a note in the participant's electronic medical record notifying his/her PCP and most recent PCMHI provider (if applicable) of the presence of anxiety symptoms. Additionally, EUC participants will receive 4 brief monthly check-in calls from study staff to review the resource list and assess current anxiety symptoms and serve as an attention control (see Appendix 9B for resource list, and Appendix 5H for EUC manual). EUC participants will receive the same study reimbursement as bCBT participants and will be asked to complete the same assessments at 4-, 8-, and 12-month follow-ups. Due to ethical concerns of withholding needed treatment, EUC participants will NOT be restricted from receiving mental health services including psychotherapy during the study period. We fully expect that EUC participants may receive anxiety treatments (e.g., antianxiety and antidepressant medications or psychotherapy).

bCBT Providers:

PCMHI providers who conduct psychotherapy as part of their VA scope of practice will be targeted for recruitment. Providers will not be restricted based on profession. PCMHI clinic directors at all three sites have agreed to support the project and will be the primary points of contact for provider recruitment. PCMHI directors will identify a local champion to further enhance recruitment and communication between the clinical site and study team. Based on the staffing at these sites and rates of provider participation in our prior trials, we expect to enroll 25 providers across the sites.¹⁰ Providers from our recently completed trial included social workers, psychologists, physician assistants, as well as psychology and social work interns and postdoctoral fellows.

bCBT Training:

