Other Demographic and Clinical Data: Demographic data will include age, gender, ethnicity, income, marital status, education, employment, and distance from the VA and/or CBOC¹⁰. Diagnosis of anxiety disorders, PTSD, and depression will be based on the MINI structured interview²¹. Each diagnosis will be dichotomized and coded as present/absent. PTSD severity will be assessed using the PTSD Checklist-Civilian Version (PCL-5²²), a standardized self-report rating scale that corresponds to DSM-5 symptoms of PTSD and possess strong psychometric properties. Medical complexity will be calculated using the Charlson Comorbidity Index (CCI) as defined by VA database extractions for the 12 months prior to the baseline date. The Charlson score has been widely used in the literature for assessing morbidity and mortality^{23,24}. Psychotropic medications will be collected through VINCI databases following procedures used

in the team's prior work^{10,11,25}. Medication tracking will include information on start date of medication, dose, and days-supply. Medication use will be coded for presence or absence and changes in type or dosage. We will monitor medications use in both bCBT and EUC groups through database extraction after the 12-month assessments to allow us to determine whether assignment to bCBT affected receipt of medications. Mental health service use: Mental health service use will be monitored for each participant to allow us to control for non-bCBT mental health service use. We will collect data via review of VA medical records as well as from a self-report non-VA service-use questionnaire (Appendix 6G). We will use CDW to capture data on emergency room visits and hospitalizations and will compare the frequency and types of such visits between arms (and between in-person and VVC-H bCBT encounters) quarterly. We will involve clinical leadership and the IRB if there are between-group differences in these safety measures.

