To compare changes in anxiety symptoms between the two groups over time, we will use a longitudinal, mixed-model analysis containing terms for the intercept, treatment, time, and interaction between time and treatment. In separate analyses, we will compare changes in quality-of-life between the two groups over time using a similar mixed-model approach. The mixed-model analysis will allow us to nest patients by site. Any baseline characteristics found to be significantly different between bCBT and EUC will be included in the model, *as will any differences in mental health service use*. The four time points (baseline, 4-, 8-, and 12-month) will allow us to assess the immediate impact of treatment and the longer-term retention, improvement, or decay in outcomes. The treatment effect will measure differences between the intervention and control groups at baseline, and the time effect will measure whether there was an overall change over time in the outcome. The term of most interest will be the interaction between time and treatment, which will indicate whether there is a difference over time between the two groups. The use of the random-coefficient model will allow us to fit a line for each participant using his/her available data, including participants with missing values, and maximize the power to detect differences.

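### The primary model adjusts for mental health service use after randomisation, which can move the time-by-treatment estimate off the declared intention-to-treat effect

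*Protocol*

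**What the plan says.** Protocol section 5.6 opens the primary analysis with this commitment: "All analyses will be done on an intention-to-treat basis, and participants will be analyzed in the group to which they were randomized". The primary model is a longitudinal mixed model over four visits (baseline, 4, 8 and 12 months) with treatment, time and their interaction. Patients are nested by site, and the interaction is the term of main interest.

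The same section then sets the covariates: baseline variables with a significant arm difference "will be included in the model, as will any differences in mental health service use". The SAP's Primary aim text has the same rule: "Any baseline characteristics found to be significantly different between bCBT and EUC will be included in the model", followed by "as will any differences in mental health service use". Neither document says what counts as a difference in service use or whether the term is time-constant, time-varying or interacted with time. Neither names a model without it as primary.

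Protocol section 5.5 gives the purpose: "Mental health service use will be monitored for each participant to allow us to control for non-bCBT mental health service use". Table 4 marks the health service use extraction in the 12-month column only.

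On the comparator, section 5.1 states: "EUC participants will NOT be restricted from receiving mental health services including psychotherapy during the study period". The same section gives EUC participants a letter urging them to raise treatment with their VA providers and monthly calls that go over a resource list. It says openly that they may be treated elsewhere.

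**The concern.** Care sought after randomisation is partly a result of the assignment. It is also part of what enhanced usual care means in this trial. A model that holds it equal across arms asks what bCBT would do if both arms used the same amount of other care. That is not the effect of assigning patients to bCBT or EUC.

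Service use also follows symptoms. Section 5.1 lets bCBT clinicians refer patients who miss the anxiety goal to therapies outside the study. A covariate that partly records failure to improve mixes prognosis into the treatment comparison, and randomisation no longer protects against that.

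At stake are the size and the significance test of the headline result. The rule is triggered by the trial's own data, so the final model is not known in advance.

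**Working it through.** **Is the variable measured after randomisation?** The sentence in section 5.6 does not say so, but three places point that way:
- Section 5.5 defines it as care other than bCBT, a distinction that has meaning only once treatment starts.
- Table 4 places the extraction at 12 months.
- Section 5.4 excludes current psychotherapy for anxiety, so arm differences in that care arise after assignment.

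**Inputs.** From the protocol: 145 bCBT and 80 EUC, effect 0.38 SD, correlation 0.7. Assumed, because the documents give no figures: service use of 40% or 50% in EUC and 20% in bCBT. The plan has no figure of its own to reproduce on this point. Negative values favour bCBT.

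**Case A: other care helps by 0.4 SD and is unrelated to prognosis.** The intention-to-treat effect is the direct effect plus (benefit of care) × (difference in use). Adjustment returns the direct effect.
- 40% v 20%: −0.38 − (−0.4)(0.2 − 0.4) = −0.38 − 0.08 = −0.46.
- 50% v 20%: −0.38 − (−0.4)(0.2 − 0.5) = −0.38 − 0.12 = −0.50.

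**Case B: other care does nothing, but its users are those getting worse.** Assume that the tendency to use care correlates 0.5 with an unmeasured factor that carries 0.6 × √0.51 = 0.43 SD of the follow-up score. The within-arm slope of outcome on use is covariance divided by variance. The covariance is 0.43 × 0.5 × the weighted normal density at each arm's usage threshold. The variance is the weighted p(1−p).
- 50% v 20%: covariance = 0.4285 × 0.5 × (145 × 0.280 + 80 × 0.399)/225 = 0.0690; variance = (145 × 0.16 + 80 × 0.25)/225 = 0.192; slope = 0.360. Shift = 0.360 × 0.3 = 0.108, so the estimate is about −0.27.
- 40% v 20%: covariance = 0.0681; variance = 0.188; slope = 0.361. Shift = 0.361 × 0.2 = 0.072, so the estimate is about −0.31.

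**Simulation of change from baseline (5,000 trials per row)**

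| Case | Use, EUC / bCBT | Unadjusted (truth −0.38) | Adjusted for use | Rejection at true null, adjusted |
|---|---|---|---|---|
| A | 40% / 20% | −0.382 | −0.461 | 11.2% |
| A | 50% / 20% | −0.382 | −0.502 | 18.1% |
| B | 40% / 20% | −0.377 | −0.305 | 10.4% |
| B | 50% / 20% | −0.382 | −0.273 | 15.8% |

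Without adjustment, null rejection was 4.7-5.4%.

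**Four-visit model, service use interacted with time.** At a true null the case B estimate was 0.090 (40% v 20%) and 0.123 (50% v 20%). The second shift takes −0.38 to about −0.26, which is the lower end of the range quoted. Three further results set the limits:
- With both mechanisms at once, the shift was about 0.005 (0.011 against 0.006 unadjusted at 40% v 20%; 0.005 against −0.001 at 50% v 20%).
- With equal use in both arms (40%), the shift was at most 0.002.
- With more use in bCBT (50% v 30% in EUC), the signs reversed: 0.072 in case A and −0.080 in case B.

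**Four-visit model, service use as a time-constant main effect.** With complete data the interaction was identical to the unadjusted one to three decimals in these scenarios. Such a term explains differences in level between participants, while the interaction is a contrast of change. With about 25% outcome-dependent dropout, the interaction moved by less than 0.005 SD.

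**Baseline covariates chosen by significance.** Selecting from eight variables at p < 0.05 gave mean estimates of −0.38 and 0.00 for true effects of −0.38 and 0, with null rejection of 4.0-4.9%. The chance that at least one of K independent tests is significant is 1 − 0.95^K: 23% for K = 5, 26% for K = 6 and 40% for K = 10. The 0.05 threshold is assumed; the plan states none.

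**The case against.** The strongest defence is that section 5.6 lists only intercept, treatment, time and their interaction, and no product of service use with time. Read literally, service use would be a plain main effect, and the term of interest would hardly move. That is correct for that form. But the plan does not choose the form, and a variable built up over follow-up could naturally be coded as time-varying. If the main effect is what is meant, the clause does nothing for the estimate and there is no reason to keep it.

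It can also be said that the cases above are extremes, that real use would probably both help and follow severity, and that the effects then largely cancel. That stands as a limit on the size. It gives no assurance, because the balance cannot be known beforehand.

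Section 5.6 also plans 12-month differences and effect sizes against EUC with no adjustment mentioned. Nothing makes these primary.

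Three stronger inferences are tempting but unsupported:
- That the chart note drives EUC patients to other care. Section 5.1 gives a note to all randomised participants; the letter and the calls are what is specific to EUC.
- That choosing baseline covariates by significance takes the estimate off the intention-to-treat effect. In a linear model it does not, as the simulation shows.
- That site and baseline GAD-7 enter only if they happen to differ. Patients are already nested by site, and baseline is already the first of the four outcome visits.

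**Conclusion.** The service-use clause conflicts with the declared intention-to-treat analysis in both documents and should leave the primary model. A reader might conclude that the primary estimate is certain to be biased. The documents do not support that. A shift needs both an arm difference in use and a term that acts on follow-up change.

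Under those conditions and the assumed rates, a true 0.38 SD effect could be reported as about 0.26 to 0.50 SD, which is (0.38 − 0.26)/0.38 = 32% too small to (0.50 − 0.38)/0.38 = 32% too large. A true null could be rejected in 10-18% of trials. These figures are illustrations and depend on usage rates and mechanisms that the documents do not give. In case A the adjusted model estimates a legitimate quantity, the effect at equal service use, but it is the wrong one for the stated hypothesis.

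The baseline-covariate rule is a separate, lesser fault. It makes the model depend on the data and picks variables by chance imbalance, not by how well they predict outcome. Baseline anxiety is among the variables tested, so it could also enter twice: as a covariate and as the first outcome visit.

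**What to change.** In Protocol section 5.6 and the SAP's Primary aim text:

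1. Delete the clause "as will any differences in mental health service use" from the primary model. Align the stated purpose in section 5.5 ("to allow us to control for non-bCBT mental health service use") with this.
2. Report mental health service use and medication by arm. Label any model that adjusts for service use as exploratory or sensitivity, and state the form in which service use enters.
3. Replace the significance-based rule with a short prespecified list of baseline covariates chosen for prognosis. Keep site as already planned.
4. Use the baseline outcome once: either as the first of the four outcome visits, or as a covariate with the three follow-up visits as outcomes.

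The cost is wording in the two documents. Data collection and the planned 225 participants are unaffected. In the simulations, the model without service use recovered the true effect on average (−0.38 and 0.00), with null rejection of about 5%.
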